All data collection and on-ground study activities will be carried out by the study team in Uganda. This team will include a team leader, two lead interviewers, and three supporting team members. The design of the data collection instruments and protocols, the quality monitoring of the qualitative and quantitative data, and the data analysis will be carried out by the study team based in the United States (U.S.). Data collected on the ground will be transferred to the US team on a weekly basis through a secure web portal (Kiteworks).

Published material will be free of any personally identifying information. There is no data monitoring committee since the trial was deemed minimal risk. The study team in the U.S. will still perform data monitoring and quality assurance exercises weekly during the nine-month study period.

Handling Missing Data and Attrition

Missing data for some variables will be imputed if a participant remained enrolled in the study. When participants drop out, multiple logistic regression models will be fit to assess whether this dropout is random. If it is not, "nonresponse" weights using logistic regression will be developed to correct for dropout. All analyses will reflect these design effects in the calculation of standard errors and statistical tests of significance.

Results

This pilot study has been funded by the National Institutes of Mental Health in the United States (R34MH122331) and approved by the RAND Human's Subjects Protection Committee (2020-N0632), Mildmay Uganda Research Ethics Committee (0701-2021), as well as the Uganda National Council for Science and Technology (HS128ES). As of February 18, 2022, recruitment was completed. As of August 23, 2023, all the data collection activities were also marked completed; the analyses of the data are ongoing.

Discussion

Expected outcomes

We hypothesize that our two intervention groups will display higher mean medication adherence and higher routinized medication adherence (i.e., pill-taking within +/- one hour of participants' chosen anchor) during the three-month intervention relative to the control group. After more frequently using their anchoring strategy, we then hypothesize that our two intervention groups will better maintain their mean medication adherence and routinized medication adherence over the six months after the intervention is withdrawn. Finally, we hypothesize that our second treatment group that receives both text message reminders and small incentives for using their anchor during the three-month intervention will more strongly maintain their mean medication adherence and routinized medication adherence during the six-month post-intervention period.

Comparison to prior work

INMIND has a strong scientific premise that addresses a critical knowledge gap in the literature around the design of interventions for establishing and maintaining long-term behavior change. A growing literature in the field of psychology targets long-term behavior change [18,43]; however, most of the intervention methods are one-off interventions that do not support participants during the approximately three-month routinization process [17,20,54,55]. Behavioral economics-based interventions have also had limited efficacy in maintaining long-term behavior change. For example, incentives have successfully changed a range of health behaviors by countering present bias [38–41], including improved ART adherence [42], but these interventions typically show only short-term impact that dissipates after the incentives are withdrawn [38,43]. In our own prior studies, we also found that incentives did not have persistent effects, and only participants who showed timely adherence (an indicator that they potentially

anchored pill-taking to an existing routine) maintained high adherence after the incentives were withdrawn [44].

Our combined intervention approach attempts to leverage the successful components of these existing psychology and behavioral economics-based interventions to better maintain ART adherence. If successful, this intervention will help to expand the understanding of the habit formation process and the common psychological barriers to successfully stick to new health behaviors. The study also addresses biological variables such as age and sex appropriately and incorporates them in both the impact analysis and when testing for age and sex differences in behavioral biases and intrinsic motivation. Such analyses will be especially useful in designing a large-scale intervention that can assist all treatment initiators with establishing and maintaining long-term ART adherence.

Limitations

The study is not without limitations. First, the study will sample from one clinic in Uganda, limiting the generalizability of our results. Second, the small sample size limits the team's ability to detect clinically meaningful effect sizes. While this is not the intended aim of this feasibility and acceptability study, the small sample size is still a limitation to the statistical analyses. Third, ART adherence will only be measured over nine months, so future research will be needed to assess ART adherence over longer durations. Fourth, ART adherence will be measured using MEMS caps, which is currently one of the most accurate ways to measure medication adherence, but conscious manipulation of the pill bottle openings by the participants is still a possibility that may lead to an overestimation of the study's adherence outcomes for participants in the Incentives group who may use deception to increase their chances of a prize drawing.

Dissemination and Future Directions

The team will use peer-reviewed publications and conference presentations as the primary means of results dissemination. The findings will be relevant to those interested in the behavioral mechanisms that underly successful long-term ART adherence, and more broadly, the mechanisms underlying long-term behavior change. Additionally, the findings will be utilized in the design of a larger-scale randomized controlled trial that we will use to rigorously assess the effectiveness of the INMIND intervention for establishing long-term ART adherence habits. In addition to future randomized controlled trials, we plan to use the detailed MEMS data on the

timing of daily pill-taking to inform statistical models of the habit formation process, which will guide new intervention designs for promoting ART adherence habits.

Data Availability

De-identified research data will be made available, along with the survey instruments, to interested external researchers through collaborative agreements with the PI and co-investigators, as required by the National Institutes of Health's data sharing policies.

Trial status

The trial was retrospectively registered on Clinicaltrials.gov (registration number: NCT05131165) on 12 November 2021. The study start date was 25 October 2021, and the protocol was last updated on 22 September 2022. The primary completion date was 23 August 2023, and the study completion date is expected to be in August 2025.

List of abbreviations

AIDS: acquired immunodeficiency syndrome

ART: antiretroviral therapy

HIV: human immunodeficiency virus MEMS: medication event monitoring system

SPIRIT: standard protocol items: recommendations for interventional trials

References

2. Parienti J-J, Ragland K, Lucht F, de la Blanchardière A, Dargère S, Yazdanpanah Y, Dutheil J-J, Perré P, Verdon R, Bangsberg DR. Average adherence to boosted protease inhibitor therapy, rather than the pattern of missed doses, as a predictor of HIV RNA replication. *Clinical Infectious Diseases* 2010;50(8):1192–1197.
4. Pasternak AO, de Bruin M, Jurriaans S, Bakker M, Berkhout B, Prins JM, Lukashov VV. Modest nonadherence to antiretroviral therapy promotes residual HIV-1 replication in the absence of virological rebound in plasma. *The Journal of Infectious Diseases* 2012;206(9):1443–1452.

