We propose to test the intervention “INcentives and ReMINDers to Improve Long-term Medication Adherence” (INMIND) in a pilot, parallel group randomized controlled trial (RCT) at the Mildmay Uganda HIV clinic in Kampala, Uganda with two intervention groups and a control group using an even allocation ratio of 1:1:1 between the three study groups. All participants (including in the control group) will receive information about the importance of behavioral routines, as is part of the standard adherence counseling for treatment initiators at Mildmay Uganda and will create personalized ART adherence anchoring strategies. The first intervention group will additionally receive text message reminders of their anchoring strategy, and the second intervention group will receive both the text message reminders and small incentives conditional on taking ART pills within a time window that corresponds to participants’ personalized anchoring strategy. We hypothesize that the text message reminders and incentives will increase participants’ use of their anchoring strategy, and thus medication adherence will be better maintained after the intervention ends in our two intervention groups relative to the control group. We also expect to see stronger maintenance in the intervention group receiving both reminder messages and incentives than the intervention group receiving only reminder messages.

Methods

Ethics Approval

This pilot RCT has been funded by the National Institutes of Mental Health in the United States (R34MH122331) and approved by the RAND Human’s Subjects Protection Committee (2020-N0632), Mildmay Uganda Research Ethics Committee (MUREC) (0701-2021), as well as the Uganda National Council for Science and Technology (HS128ES). As of February 18, 2022, recruitment was completed.

Study Design

This study will use a three-armed randomized controlled trial (two intervention groups and one control group) with randomization at the individual level. The interventions will be administered for a period of three months from the baseline survey. During the intervention period, MEMS data readings will be collected monthly, wherein prize drawings for eligible participants in the Incentives group will be carried out. Since the population of interest are treatment initiators, the monthly study visits are expected to coincide with the monthly clinic visits as mandated for

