newly diagnosed clients who are getting accustomed to ART treatment. During the post-intervention period, the team will follow participants and continue MEMS data collection during the participants' regular clinic visits (expected to be every month for the first six months post treatment initiation, and every one-to-three months thereafter) for a period of six months, bringing the total study period to nine months.

Since the long-term goal of the study is viral suppression, viral load data will also be collected during the routine assessment. Viral load tests for treatment initiators are conducted after the first six months of ART initiation, and then switched to 12-month periods as per clinic and Ugandan Ministry of Health guidelines. Survey assessments will be administered at baseline, month three, and month nine for all participants.

It is important to note that the pilot study is being preceded by a formative phase, and succeeded by an adaptation phase, both of which are geared towards collecting qualitative data pertaining to the overall design, feasibility, and acceptability of the interventions. The results of the formative phase will be used to adapt the pilot intervention materials and timeline prior to the intervention administration. The adaptation phase is expected to provide feedback on the mission critical parameters of the interventions, which would be utilized to mold the intervention in preparation for a full-scale randomized controlled trial. Figure 2 gives the timing of study activities.

Study Sites

The study will be performed at the Mildmay, Uganda, an HIV clinic in Kampala, Uganda. This clinic specializes in providing comprehensive HIV and AIDS prevention, care, and treatment services to over 105,000 HIV-infected patients. It offers integrated health services to a diverse population base; of the 15,000 patients served at the main site in Lweeza, 11% are children younger than 18 years, 65% are female, and 100% of patients are on ART. Mildmay also has well-established electronic medical records infrastructure, making it one of the growing number of facilities using electronic medical record systems in Uganda.

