Apart from the patient-facing work, Mildmay also provides technical assistance to organizations and governments, hosting training and educational courses for over 1,500 professionals per year. Further, the Mildmay Uganda laboratory is accredited by the South African National Accreditation System under ISO 15,189:2012, and specializes in virology and other tests.

Mildmay also has numerous ongoing research projects involving international researchers. It has a standing Community Advisory Board comprising of church leaders, elected councilmen, healthcare providers (external to Mildmay), and HIV client advocates.

Sampling Strategy

The objective of this study is to establish preliminary efficacy as well as acceptability and feasibility of the interventions. Consequently, 150 participants will be recruited from Mildmay's main site for the pilot study. The sample will be representative of the patient population at Mildmay with a roughly 70:30 ratio of female to male clients.

Electronic medical records and the hospital electronic database will be used to screen the client population for initial eligibility based on age and ART initiation period, as noted in the Eligibility Criteria below. For this step, the hospital staff (and not the study coordinator) will mine the electronic database for this information to create a master list of eligible clients. Given the focus on treatment initiators, this process will be carried out weekly to identify newly diagnosed clients who are eligible to participate in the study.

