A daily list of expected clients will be generated from the master list for the study coordinators to locate those deemed eligible and who are due for a clinic visit. Once a client is located, a pre-baseline visit will be initiated with the study coordinator approaching the client and inquiring about their interest in participating in an ongoing study. On confirming interest, clients will be taken to a separate study room to verify their eligibility, and to receive their consent to participate. Consented participants will be given a medication event management system (MEMS) cap and instructed to store one of their HIV medications in a pill bottle with the MEMS cap attached. Additionally, they will be given a study appointment after approximately one month of this initial visit for adherence data retrieval and baseline survey administration. The first month of adherence data will be used as a baseline and the intervention will not begin before this follow-up visit.

Inclusion Criteria

The study sample will consist of male and female clients aged 18 and older who have started ART at Mildmay within the preceding three months. Treatment initiation is an important eligibility criterion given the conceptual framework of the pilot, which suggests that habit formation during initiation is a key driver for sustained ART adherence over time. Based on electronic records

data from Mildmay, each month at least 100-150 clients with these characteristics begin treatment at the hospital (for a total of 1,758 in 2018); therefore, a large pool of potentially eligible clients will be available for recruitment. Given the nature of the intervention, inclusion will also require participants to own, or have access to a phone at least five days a week throughout the duration of the intervention, while being willing to receive text messages throughout the intervention period.

Exclusion Criteria

Children under the age of 18 were excluded for two reasons: 1) the pediatric clinic is separate from the main recruitment site (which primarily caters to adult clients), and 2) the intervention might require alteration to account for the specific needs of children and adolescents.

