Additionally, clients who are not mentally fit to understand the consenting or study procedures, as well as clients who speak neither English nor Luganda (the local language spoken by the majority of people in and around Kampala) were excluded. As both intervention groups rely on the receipt of text messages, clients who don't own a cell phone or have access to one will also be excluded.

Participation in another adherence study as well as non-ability or non-desire to use MEMS caps regularly throughout the course of the study will also be a basis for exclusion. Consequently, if the baseline MEMS reading suggests that participants opened their pill bottle less than 30% of days, and if that was not a consequence of low adherence, then the participant will be given a transport refund and will be unenrolled from the study. Finally, clients coming outside regular clinic working hours will be excluded.

Randomization and Allocation

Participants will be randomly assigned to either one of the treatment arms (T1 = *Messages*; T2 = *Incentives*) or the control arm after consenting but will only be informed of their assignment after the baseline survey is over to minimize any potential influence of the assignment on the baseline survey responses. The distribution ratios for the randomization will be 1:1:1 and the assignment will be carried out through a computer-generated randomization component built into the baseline survey administration software, called Questionnaire Development System. The random assignment (to either the control group or one of the two intervention arms) will be revealed at the end of the baseline survey to both the participant and the study coordinator, who will therefore not know the respondent's treatment assignment during the survey. Given the

nature of the intervention, neither the interviewers nor the participants can be blinded to the treatment status. However, the data analyst who will conduct the impact analysis will be blinded to treatment assignment.

Procedures

Interventions

The pilot will include a control arm, along with two intervention arms – *Messages* (T1) and *Incentives* (T2).

Control Group: Usual Care

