The recruitment (or pre-baseline) visit will be used as an opportunity to screen the clients. Once the client is found to meet the initial eligibility criteria, s/he will be given a MEMS cap, which will be used to track baseline adherence and study eligibility for approximately one month. In case their clinic visit does not coincide with the expected study visit, participants will be provided a study visit appointment and will be told that they will receive travel compensation for making the additional trip. Clients will also be consented to participate during this initial recruitment visit.

Months 1-3 Visits

During the three-month intervention period, participants will be scheduled for monthly clinic appointments and the study coordinators will a) collect information on changes or degradations of existing routine behaviors; b) conduct prize drawings with the *Incentive* group; and c) update contact information in case phone numbers or addresses have changed. After the first three months, this information will be collected during the participants' regular clinic visits. When participants report the degradation of their selected behavioral anchor, a new daily routine will be identified for the anchoring strategy from the suggested list of three common routine behaviors.

Post-Intervention Surveys

Follow-up surveys will be administered at month three (i.e., at the end of the intervention) and month nine (i.e., six months after the end of the intervention) to evaluate behavioral persistence. These surveys will be designed to evaluate how the intervention affects both the primary outcomes and secondary outcomes, as well as cognitive and motivational factors that may be influenced by the intervention. Intervention effects over the nine-month study period will also be assessed as these effects might be most pronounced in the first months when the pill-taking routine is first established but then taper off as the novelty of the intervention fades or anchoring routines are changed. The post-intervention assessment will happen during a scheduled hospital visit to avoid participants having to make costly additional hospital visits specifically for interviews.

Data Collection Methods

Surveys

The baseline survey contains questions pertaining to:

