Feasibility and acceptability will be analyzed using summary statistics derived directly from our self-reported measures. To estimate preliminary efficacy, statistical analyses comparing group-level differences in the secondary and tertiary outcome measures will be performed. An Analysis of Covariance framework will be used to test for group differences in each secondary and tertiary outcome, controlling for the participant characteristics that are found to differentiate the groups at baseline. For analyses of dichotomous variables, such as viral suppression, a non-parametric McNemar's test and an analogous multiple logistic regression will be used to control for covariates to assess group differences. In addition to static comparisons of group means for each outcome at three-month intervals, the longitudinal nature of the data will be leveraged by using repeated measures and time-series techniques. Specifically, a linear mixed model with repeated observations will be fit using maximum likelihood through 'xtmixed' in the

software package Stata to study group-level temporal dynamics in daily measures of the primary and secondary outcomes.

Sample and Effect-size Estimation

We will recruit a total of 150 participants and will assume a 90% retention rate through the 9-month study period. This is a conservative estimate of attrition, as previous research in the same clinic and with a similar population observed only 6% attrition over 12-month study periods [44,48]. Given the study objectives of establishing acceptability, feasibility, and preliminary effectiveness, the targeted sample size may not have the power to detect many of the effects that would be clinically significant. Nonetheless, effect size calculations associated with 80% power (2-tailed test) with regard to the primary outcomes at month nine have been carried out. A recent study conducted at Mildmay suggested that mean ART adherence rates are ~ 75% (SD = 20) as measured by MEMS caps [44]. Using these parameters as estimates of adherence for the control group, and 10% attrition at month nine, a sample size of 150 will provide sufficient power to detect a 9% difference in mean adherence between the pooled intervention groups and the control group (effect size = .47), and a roughly 11% difference in mean adherence between the two intervention groups. This translates to the study being able to detect medium effect sizes.

Qualitative Analysis

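### The power statement allows nothing for losses between recruitment and allocation, and on its stated inputs the detectable differences at 135 analysed are 10.2 and 11.8 points, not 9 and roughly 11

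*Combined protocol and SAP*

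**What the plan says.** All references are to the combined protocol and SAP.

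- **Number.** Sampling Strategy: "Consequently, 150 participants will be recruited from" the clinic's main site. Sample and Effect-size Estimation: "We will recruit a total of 150 participants and will assume a 90% retention rate through the 9-month study period".
- **When recruitment happens.** Study Timeline, Recruitment: "The recruitment (or pre-baseline) visit will be used as an opportunity to screen the clients". Consent is taken and the MEMS cap issued at that visit. Figure 2 lists both under enrolment, ahead of allocation.
- **What follows.** Under Sampling Strategy, consented participants leave with a cap and "they will be given a study appointment after approximately one month of this initial visit for adherence data retrieval and baseline survey administration". Randomization and Allocation puts the assignment inside the baseline survey software and reveals it when the survey ends.
- **Losses in between.** Under Exclusion Criteria, if the baseline cap reading shows openings on fewer than 30% of days and low adherence is not the reason, "then the participant will be given a transport refund and will be unenrolled from the study".
- **When the nine months start.** Study Design: "The interventions will be administered for a period of three months from the baseline survey". Post-intervention follow-up then continues "for a period of six months, bringing the total study period to nine months".
- **Power claim.** Sample and Effect-size Estimation takes mean adherence of about 75% with SD 20, 80% power and a two-tailed test: "Using these parameters as estimates of adherence for the control group, and 10% attrition at month nine". It reports detectable differences of 9 points for the pooled intervention arms against control (effect size 0.47) and roughly 11 points between the two intervention arms. Alpha is not stated there.

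**The concern.** The 150 appears to be counted about a month before the period to which the 10% loss applies. The plan itself expects people to leave in that month: some will not return, and one rule removes participants on their baseline cap reading. The sizing budgets nothing for either, and no replacement rule is written.

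Two things are at stake. The printed detectable differences may rest on more participants than reach month nine. Also, study retention is a feasibility measure, and this pilot is meant to inform a full-scale trial. A sample size that omits the loss between recruitment and allocation would carry the same gap forward.

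**Working it through.** **Inputs.** From the plan: 150 recruited, 10% attrition, 1:1:1 allocation, SD 20, 80% power, two-tailed test. Assumed: alpha 0.05, a normal approximation, equal SDs, and no variance reduction from covariates.

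**Step 1: number analysed as the plan has it.** 150 × 0.90 = 135, or 45 per arm. The contrasts are 90 against 45 (pooled against control) and 45 against 45 (between intervention arms).

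**Step 2: try to reproduce the stated differences.** Detectable difference = (1.960 + 0.842) × SD × √(1/n₁ + 1/n₂).

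- Pooled against control: 2.802 × 20 × √(1/45 + 1/90) = 56.03 × 0.1826 = **10.2 points** (d = 0.51). The plan states 9 (0.47, which is 0.47 × 20 = 9.4 points).
- Between intervention arms: 56.03 × √(2/45) = 56.03 × 0.2108 = **11.8 points**. The plan states roughly 11.

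Neither stated figure is recovered. Power = Φ(difference / (20 × √(1/n₁ + 1/n₂)) − 1.960):

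- 9 points: 9/3.651 − 1.960 = 0.505, so 69%.
- 9.4 points: 9.4/3.651 − 1.960 = 0.614, so 73%.
- 11 points: 11/4.216 − 1.960 = 0.649, so 74%.

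**Step 3: other routes to the stated figures.**

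| Assumption | Pooled vs control | Between intervention arms | Compared with the plan |
|---|---|---|---|
| 150 analysed, no attrition | 9.7 | 11.2 | Only the second matches; drops the 10% loss |
| One-sided 0.05, 135 analysed | 9.1 | 10.5 | Contradicts the two-tailed test |
| Equal split of 135 | 9.6 | not applicable | Contradicts 1:1:1 |
| Adjustment for a baseline covariate correlated 0.4 with the outcome | 9.4 | 10.8 | Close to both, but no correlation is stated |

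The last row is the Step 2 result times √(1 − 0.4²) = 0.917.

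**Step 4: add a pre-allocation loss L.** The documents give no rate, so L is an assumed range. Analysed N = 150 × (1 − L) × 0.90, and the Step 2 differences grow by 1/√(1 − L).

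| L (assumed) | Analysed | Pooled vs control | Between intervention arms | Power at 9 | Power at 11 |
|---|---|---|---|---|---|
| 0% | 135 | 10.2 | 11.8 | 69% | 74% |
| 5% | 128 | 10.5 | 12.1 | 67% | 72% |
| 10% | 121.5 | 10.8 | 12.5 | 65% | 70% |
| 20% | 108 | 11.4 | 13.2 | 60% | 65% |

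**Step 5: how much loss could be absorbed?** The plan cites 6% attrition in earlier research at the clinic (Sample and Effect-size Estimation) and about 5% (Participant Tracking). If later attrition were at those levels, 135 would still be reached with a pre-allocation loss of up to 1 − 135/(150 × 0.94) = 4.3%, or 1 − 135/(150 × 0.95) = 5.3%.

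**The case against.** **The counting point is inferred.** The control-group description uses the word recruitment for the leaflet and anchor steps, which the Messages description places at the reveal of assignment. The 30% cap rule sits under Exclusion Criteria, so someone it removes could be regarded as a screening failure and not one of the 150. With at least 100–150 eligible starters a month (Inclusion Criteria), continuing until 150 were allocated was feasible. If 150 means allocated, pre-allocation loss does not reduce it. This stands as a real ambiguity. Study Timeline's wording still makes the pre-baseline visit the more natural reading, and nothing in the plan says that losses would be replaced.

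**Text-message registration.** A reader might also count participants unenrolled because registration was not confirmed. That happens after the arm is revealed, so it may already fall within the 10%. It is left out here.

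**Run-in loss as the cause.** A reader might infer that pre-allocation losses certainly leave fewer than 135, and that this is why the stated differences are too small. The documents support neither step. No run-in rate is given, and Step 5 shows that a loss of 4–5% could be absorbed. The differences already fall short at the full 135. For the same reason, scaling 9 and 11 upward for run-in loss would start from figures that do not reproduce.

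**Covariate adjustment.** The analysis is an ANCOVA, and a correlation near 0.4 would come close to both stated figures. But the sizing mentions no adjustment, and the planned covariates are whichever characteristics differ between groups at baseline. The stated figures cannot be credited on that basis unless the assumption is written down.

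**Materiality.** The plan already admits limited power, recruitment is complete, and no analysis would change. That limits the importance of the point. It does not make the printed figures right.

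**Conclusion.** The point holds with limits. On the most natural reading, the sizing starts from 150 people at the pre-baseline visit and allows only for losses after the baseline survey. Non-return and cap-rule unenrolment before allocation have no allowance. A month-nine number below 135 is likely but not established.

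The firmer finding does not depend on run-in loss. On the plan's stated inputs, with alpha 0.05 assumed and no covariate adjustment, the detectable differences at 135 are 10.2 points (d = 0.51) and 11.8 points, against the stated 9 (0.47) and roughly 11. Assumed pre-allocation losses of 5–20% would raise them to 10.5–11.4 and 12.1–13.2 points. This is a minor correction to a pilot's power statement and does not threaten its conduct or analysis.

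**What to change.** - State the sample size as participants allocated at the end of the baseline survey.
- Recompute and restate both detectable differences from the number actually allocated, which should be known now that recruitment is complete. Keep the 10% loss after allocation, and state alpha and any covariate adjustment assumed.
- Report the loss between recruitment and allocation as its own figure, for planning the full-scale trial.

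The cost is one recalculation and a few sentences. The stated differences become slightly less favourable. No extra enrolment is needed.
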